8.2. Reporting Period

For SAEs, the active reporting period to Pfizer or its designated representative begins from the time that the patient provides informed consent, which is obtained prior to the patient's participation in the study, ie, prior to undergoing any study-related procedure and/or receiving study treatment, through and including 90 calendar days after the last administration of the study treatment (Arm A) or 90 days after the EOT visit (Arm B). SAEs occurring to a patient after the active reporting period has ended should be reported to the sponsor if the investigator becomes aware of them; at a minimum, all SAEs that the investigator believes have at least a reasonable possibility of being related to study treatment are to be reported to the sponsor.

AEs (serious and non-serious) should be recorded on the CRF from the time the patient has taken at least 1 dose of study treatment (Arm A) or from Cycle 1 Day 1 (Arm B) through and including 90 calendar days after the last administration of study treatment (Arm A) or 90 days after the EOT visit (Arm B).

If a patient begins a new anticancer therapy, the AE reporting period for non-serious AEs ends at the time the new treatment is started. Death must be reported if it occurs during the SAE reporting period after the last dose of study treatment, irrespective of any intervening treatment.

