5.2.7. Definition of on-treatment period

Safety endpoints will be summarized based on the on-treatment period unless otherwise specified. On-treatment period is defined as follows:

- Arm A: time from the first dose of study treatment through minimum (30 days + last dose of study treatment, start day of new anti-cancer drug therapy – 1 day);
- Arm B: time from Cycle 1 Day 1 through minimum (30 days + end date of BSC, start day of new anti-cancer drug therapy – 1 day).

Here, 'end date of BSC' is the date of completion or discontinuation as collected in the 'Disposition - Treatment Phase' eCRF page.

Safety data collected outside the on-treatment period as described above will be listed and flagged in listings but will not be summarized.

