6.6.1. Adverse events

Treatment-emergent adverse events (TEAEs) are those events with onset dates occurring during the on-treatment period as defined in [Section 3.5.1](#).

All analyses described below will be based on TEAEs (started during the on-treatment period) if not otherwise specified. The AE listings will include all AEs (whether treatment-emergent or not). AEs with onset outside the on-treatment period will be flagged in the listings.

- **Related Adverse Events:** adverse events with relationship to study treatment (as recorded on the AE eCRF page, Relationship with study treatment = Related) reported by the investigator and those of unknown relationship (ie, no answer to the question ‘Relationship with study treatment’).
- **Serious Adverse Events (SAE):** serious adverse events (as recorded on the AE eCRF page, Serious Adverse Event = Yes).
- **Adverse Events Leading to Dose Reduction:** adverse events leading to dose reduction of study treatment (as recorded on the AE eCRF page, Action taken with study treatment = Dose reduced).
- **Adverse Events Leading to Interruption of Study Treatment:** adverse events leading to interruption of study treatment (as recorded on the AE eCRF page, Action taken with study treatment = Drug interrupted). The eCRF does not allow for a clear separation between interruption of an infusion and delays of administration for a parenteral drug, as both are recorded using the same term on the eCRF (“Drug interrupted”). IRRs will be excluded in the analysis of AEs leading to Drug Interruption in case they only led to an interruption of the infusion.

- **Adverse Events Leading to Permanent Treatment Discontinuation:** adverse events leading to permanent discontinuation of study treatment (as recorded on the AE eCRF page, Action taken with study treatment = Drug withdrawn).
- **Adverse Events Leading to Death:** adverse event leading to death (as recorded on the AE eCRF page, Outcome = Fatal, as well as AEs of Grade 5).
- **Immune-related Adverse Events (irAE):** irAEs (as identified according to the methodology outlined in [Appendix 1](#) for a pre-specified search list of MedDRA PTs, documented in the Safety Review Plan [SRP] and finalized for analysis of the current studies data prior to DB lock)

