6.6.4. Other significant adverse events

The frequency (number and percentage) of patients with each of the following will be presented for irAEs, by treatment arm:

- irAEs leading to death, by Cluster and PT
- irAEs, by Cluster and PT
- irAEs, Grade ≥ 3 , by Cluster and PT
- irAEs leading to discontinuation of avelumab, by Cluster and PT
- irAEs leading to discontinuation of BSC, by Cluster and PT
- Serious irAEs, by Cluster and PT

The listing of all irAEs will also be provided with the relevant information with a flag for irAEs with onset outside of the on-treatment period.

The frequency (number and percentage) of patients with each of the following will be presented for IRRs, by treatment arm:

- IRRs leading to death, by PT
- IRRs, by PT
- IRRs, Grade ≥ 3 , by PT
- IRRs leading to discontinuation of avelumab, by PT
- Serious IRRs, by PT
- Time related to first onset of an IRR (infusion 1, infusion 2, infusion 3, infusion 4 or later).

The listing of all IRRs will also be provided with the relevant information with a flag for IRRs with onset outside of the on-treatment period.

In addition, the following analyses will be presented for irAEs (as defined in [Appendix 1](#)) and Tier-2 events separately. CIs for risk difference will be calculated based on the unconditional exact method by [Santner and Snell \(1980\)](#). No additional analyses will be presented for Tier-3 AEs.

- Frequency (number and percentage) of patients with each of the following by treatment arm and PT or Clustered Term:
 - Tier-2 AEs
 - Tier-2 AEs Grade ≥ 3
- Point estimate for risk difference and 95% CI for risk difference (experimental arm vs comparator arm) for each of the following by PT or Clustered Term:
 - irAEs
 - irAEs Grade ≥ 3
 - Tier-2 AEs
 - Tier-2 AEs Grade ≥ 3
- CIs reported are not adjusted for multiplicity and should be used for screening purposes only. The 95% CIs are provided to help gauge the precision of the estimates for the risk difference and should be used for estimation purposes only.

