9. APPENDICES

Appendix 1. Immune-Related Adverse Events

The MedDRA PTs and clusters for irAEs are defined in the Safety Review Plan (SRP) for avelumab.

Immune-related AEs (irAEs) will be programmatically identified as outlined in Table 16. This case definition is hierarchical, ie, each step is only checked for patients and events that have already met the prior step.

Table 16. Case Definition for irAEs

Step	Selection Criteria	Additional Notes
1	Event selected based on a list of pre-specified MedDRA PTs within clusters. These are included in the SRP as Tier1 events (Immune-mediated xxxx). If AE matches the list, then it is in for the next step	
2	AE onset during 1 st study drug administration or anytime thereafter through 90 days after last dose of study treatment.	This is regardless of start of new anti-cancer drug therapy and regardless of TEAE classifications
3	Answer in the AEECRF page to 'Was another treatment given because of the occurrence of the event' is 'YES'	
4	AE treated with corticosteroids or other immunosuppressant therapy. For endocrinopathies only: AE required hormone replacement	Look in the conmed pages for AE identifiers that match the AEs from Step 3. For each of such AEs if A) OR B) OR C) below are met then the AE is in for the next step A) conmed ATC code is in (H02A, H02B, D07, A01AC, S01BA, S01BB, L04AA, L04AB, L04AC, L04AD, L04AX, A07EA) and AEPT is in any of the irAE clusters. B) conmed ATC code is in (H03A, H03B) and AEPT is in one of the irAE clusters associated with "Immune-mediated endocrinopathies" C) conmed ATC code is A10A and AEPT is in the irAE cluster associated with "Immune-mediated endocrinopathies: Type I Diabetes Mellitus"

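### Late serious and Grade 3 or higher AEs outside the irAE definition are only listed, and the irAE risk differences count events that begin after new anti-cancer drug therapy

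*SAP*

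**What the plan says.** **Collection.** Protocol 8.2 records AEs, serious or not and regardless of cause, through 90 days after the last dose in Arm A or after the end-of-treatment visit in Arm B. There is one early stop: "If a patient begins a new anticancer therapy, the AE reporting period for non-serious AEs ends at the time the new treatment is started". SAE collection continues past that point; Protocol 5.9 says so and also requires the concomitant medications linked to those SAEs to be recorded.

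**General tables.** SAP 5.2.7 sets a default: "Safety endpoints will be summarized based on the on-treatment period unless otherwise specified". The on-treatment period ends 30 days after the last dose (Arm A) or the end of BSC (Arm B), or the day before a new anti-cancer drug if that comes first. For later data: "Safety data collected outside the on-treatment period as described above will be listed and flagged in listings but will not be summarized". SAP 6.6.1 repeats the default for AEs: "All analyses described below will be based on TEAEs (started during the on-treatment period) if not otherwise specified". SAP 6.6.3 limits the SAE tables to treatment-emergent SAEs.

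**irAE tables.** SAP 6.6.1 defines irAEs by reference to Appendix 1. Step 2 of Table 16 there accepts onset through 90 days after the last dose and adds: "This is regardless of start of new anti-cancer drug therapy and regardless of TEAE classifications". Appendix 1 also says that the resulting data set, after medical review, is what the irAE analyses use. SAP 6.6.4 plans irAE frequency tables and between-arm risk differences, plus a listing "with a flag for irAEs with onset outside of the on-treatment period".

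**Deaths.** SAP 6.6.2 tabulates all deaths by arm with the reason, as well as deaths within 30 days.

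**The concern.** Two different windows are used, and each leaves a gap.

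The general tables use about a third of the post-treatment period over which the sites report AEs. The protocol names immune-related events as an important risk of avelumab (Section 1.3), and its AE of special interest is any event suspected to be a potential irAE (Section 8.3.1). That is wider than Appendix 1. A late serious event that was suspected but did not pass the Appendix 1 algorithm would be seen only by someone reading the listings.

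The irAE window covers the full 90 days but does not stop when a patient moves to another cancer drug. The comparator is BSC, so patients who progress can be expected to start second-line treatment. The amendment history notes the accelerated US approval of atezolizumab as the reason for deleting a statement that no second-line therapy was approved, and the reference list cites a trial of second-line pembrolizumab. Immune events from such drugs can be counted in the arm to which the patient was randomised. What is at stake is the between-arm estimate of avelumab's main identified toxicity.

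**Working it through.** The plan states no figure on this point, so there is none to reproduce. The check compares windows and traces which events reach which table.

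**1. Windows after the end of study treatment**

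| Output | Last day counted | Stops at new therapy? |
|---|---|---|
| Collection, SAEs (Protocol 8.2, 5.9) | 90 | No |
| Collection, non-serious AEs (Protocol 8.2) | 90 | Yes |
| AE and SAE tables (SAP 5.2.7, 6.6.1, 6.6.3) | 30 | Yes (drug therapy) |
| irAE tables (SAP 6.6.4, Appendix 1) | 90 | No |
| All-deaths table (SAP 6.6.2) | No limit | No |

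**2. Time collected but only listed, general tables.** Let n be the day, counted from the end of treatment, on which a new anti-cancer drug starts.

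- No new drug by day 90: 90 − 30 = 60 days, for serious and non-serious events alike.
- SAEs with a new drug on day n: 90 − min(30, n − 1) days. This is 60 for n ≥ 31 and rises to 90 for n = 1.
- Non-serious AEs with a new drug on or before day 30: essentially none, because collection and tabulation stop together.

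These are days of follow-up. They are not a share of events, and they do not apply to the irAE or deaths tables.

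**3. Which late events are only listed.** Appendix 1 is hierarchical. An event must be on the preferred-term list (step 1), fall in the window (step 2), have been treated (step 3), have been treated with a corticosteroid or other immunosuppressant, or with hormone replacement for an endocrinopathy (step 4), and pass the etiology and pathology check (step 5). A non-fatal SAE or Grade 3 or higher AE on days 31 to 90 that fails any step, and is not added at medical review, reaches no table.

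**4. Can an event caused by second-line therapy pass Appendix 1 in Arm B?**

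- Step 2: yes. For Arm B the last dose of study treatment is the end date of BSC (SAP 3.4.1), and new drug therapy is expressly disregarded.
- Steps 3 and 4: yes for a serious event, since the SAE and its linked medications are still recorded.
- Step 5: this asks whether the cause is clearly something other than immune-mediated. An event from a later checkpoint inhibitor is immune-mediated. If pathology confirms an immune mechanism, the event is kept whatever the answer on etiology.

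So the algorithm can count it.

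**5. Effect on the risk difference.** Let p_A and p_B be the proportions with an irAE from study treatment. Let q_A and q_B be the proportions counted only because of an event from later therapy. Let m_A be the proportion of Arm A whose non-serious avelumab irAE began after new therapy and so was not collected. Then

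observed difference = (p_A + q_A − m_A) − (p_B + q_B) = (p_A − p_B) − [(q_B − q_A) + m_A].

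With p_A > p_B, the estimate moves towards zero when (q_B − q_A) + m_A is positive and not so large that the sign changes.

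**6. Scale.** About 668 patients randomised 1:1 gives 334 per arm. One net patient moves the difference by 1/334 = 0.30 percentage points. For orientation, Protocol 1.2.2.1 reports treatment-related potential irAEs in 71/717 = 9.9% and treatment-related pneumonitis in 8/717 = 1.1% of the pooled expansion cohorts. One net patient is then 0.30/9.9 = 3% of the overall rate and 0.30/1.1 = 27% of the pneumonitis rate. SAP 6.6.4 computes risk differences by preferred term or cluster, so the second comparison is the closer one. Those cohorts are single-arm and did not use the Appendix 1 definition, so they give scale only.

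**The case against.** A reader might infer that SAP 5.2.7 contradicts Appendix 1, and that late immune toxicity is identified and then left out of every table. The documents do not support this. The rules in 5.2.7 and 6.6.1 are defaults that allow exceptions, and Appendix 1 is such an exception: it overrides treatment-emergent status and makes its own data set the source for the irAE analyses. SAP 6.6.4 puts no treatment-emergent limit on the irAE tables, whereas 6.6.3 states one for SAEs. The flag on the irAE listing shows that out-of-window events are in the data set; it does not say that tables drop them. Late deaths are in the all-deaths table. What remains is wording: the last sentence of 5.2.7 does not repeat the exception, so a programmer could misapply the 30-day filter.

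It can also be said that a 30-day window for general tables is a pre-stated choice, that later events are still listed, that Appendix 1 filters and medical review would remove many second-line events, and that 6.6.4 presents its intervals as unadjusted and for screening. Most of this stands. The window is not an error, and the risk differences are descriptive. The filter argument is weaker: as shown above, step 5 screens for a non-immune cause. Its tick-box for medications covers prior and concomitant ones and does not mention subsequent therapy. Medical review may remove such events, but no rule is given for doing so.

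**Conclusion.** The point holds in a limited form. First, the general AE and SAE tables omit collected follow-up from day 31 to day 90 (60 days, and more for SAEs when a new drug starts early), so late serious or Grade 3 or higher events outside the irAE definition, unless fatal, are only listed. Second, the irAE risk difference mixes events before and after new therapy, under two collection rules, and can be biased towards zero.

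The size of that bias cannot be estimated from the documents. It is 0.30 percentage points per net patient affected, assuming 334 per arm in the safety set. The direction assumes that Arm B has at least as many immune events from later therapy as Arm A. That is plausible, because Arm B patients had no checkpoint inhibitor as randomised treatment, but the documents do not show it. The subsequent-therapy tables in SAP 6.5.5 would help to check it.

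Neither part touches the OS analysis or the type I error. This is a cheap improvement to the safety reporting, not a correction of an error.

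**What to change.** 1. In SAP 6.6.4, repeat the irAE frequencies and risk differences with events counted only up to the day before new anti-cancer drug therapy, using the date already derived under SAP 5.2.5. Keep the Appendix 1 version beside it, because the cut also drops genuine late avelumab events that begin after the new drug. If the two agree, later therapy is not driving the result.
2. In SAP 6.6.1 and 6.6.3, add by-arm summaries of SAEs and Grade 3 or higher AEs through 90 days. Show events after new anti-cancer therapy separately, since non-serious events are not collected there.
3. Helpful but secondary: one sentence in 5.2.7 and 6.6.4 saying that irAE tables use the Appendix 1 window.

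No further deaths table is needed. The cost is a few extra tables from data already in the CRF, with no change to conduct, data collection or the primary analysis.

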5.2.8. Standard derivations and reporting conventions

The following conversion factors will be used to convert days into weeks, months or years:
1 week = 7 days, 1 month = 30.4375 days, 1 year = 365.25 days.

Demographics and physical measurements:

- Age [years]:
 - (date of given informed consent - date of birth + 1) / 365.25;
 - In case of missing day, day only: Age [years]: (year/month of given informed consent – year/month of birth);

- In case only year of birth is given: Age [years]: (year of given informed consent - year of birth).

The integer part of the calculated age will be used for reporting purposes.

- $BMI (kg/m^2) = \text{weight (kg)} / [\text{height (m)}]^2$

For reporting conventions, mean and median should generally be displayed one more decimal place than the raw data and standard deviation should be displayed to two more decimal places than the raw data. Percentages will be reported to one decimal place. The rounding will be performed to closest integer / first decimal using the common mid-point between the two consecutive values. Eg, 5.1 to 5.4 will be rounded to an integer of 5, and 5.5 to 5.9 will be rounded to an integer of 6.

5.2.9. Unscheduled visits

Generally, data collected at unscheduled visits will be included and analyzed for both safety and efficacy analyses in the same fashion as the data collected at scheduled visits except where otherwise noted in the sections that follow. Descriptive statistics (mean, SD, median, minimum, maximum, quartiles) by nominal visit or time point for safety endpoints such as laboratory measurements, ECGs and vital signs will include only data from scheduled visits.

5.2.10. Adequate baseline tumor assessment

Adequate baseline is defined using the following criteria:

- All baseline assessments must be within 28 days prior to and including the date of randomization.
- For patients with evidence of disease at baseline, all documented lesions must have non-missing assessments (ie, non-missing measurements for target lesions and non-missing lesions assessment status at baseline for non-target lesions).

5.2.11. Adequate post-baseline tumor assessment

An adequate post-baseline assessment is defined as an assessment with no evidence of disease (for patients with no evidence of disease at baseline) or where a response of CR, PR, SD, non-CR/non-PD, or PD can be determined (see [Section 6.2.2.3](#)). Time points where the response is not evaluable (NE) or no assessment was performed will not be used for determining the censoring date.

5.3. Methods to Manage Missing Data

5.3.1. Missing data

Unless otherwise specified, all data will be evaluated as observed, and no imputation method for missing values will be used.

In all patient data listings imputed values will be presented. In all listings imputed information will be flagged.

Missing statistics, eg when they cannot be calculated, should be presented as 'ND' or 'NA'. For example, if N=1, the measure of variability (SD) cannot be computed and should be presented as 'ND' or 'NA'.

5.3.1.1. Pharmacokinetic concentrations

Concentrations Below the Limit of Quantification

For all calculations, figures and estimation of individual pharmacokinetic parameters, all concentrations assayed as below the level of quantification (BLQ) will be set to zero. The BLQ values will be excluded from calculations of geometric means and their confidence intervals (CIs). A statement similar to 'All values reported as BLQ have been replaced with zero' should be included as a footnote to the appropriate tables and figures.

Deviations, Missing Concentrations and Anomalous Values

In summary tables and plots of median profiles, concentrations will be set to missing if one of the following cases is true:

1. A concentration has been reported as ND (ie, not done) or NS (ie, no sample);
2. A deviation in sampling time is of sufficient concern or a concentration has been flagged as anomalous by the clinical pharmacologist.

Summary statistics will not be presented at a particular time point if more than 50% of the data are missing. For analysis of pharmacokinetic concentrations, no values will be imputed for missing data.

5.3.1.2. Pharmacokinetic parameters

Whether actual or nominal PK sampling time will be used for the derivation of PK parameters will be determined by the results of interim PK analyses. If a PK parameter cannot be derived from a patient's concentration data, the parameter will be coded as NC (ie, not calculated). NC values will not be generated beyond the day that a patient discontinues.

In summary tables, statistics will be calculated by setting NC values to missing. Statistics will not be presented for a particular treatment if more than 50% of the data are NC. For statistical analyses (ie, analysis of variance), PK parameters coded as NC will also be set to missing.

If an individual patient has a known biased estimate of a PK parameter (due for example to a deviation from the assigned dose level), this will be footnoted in summary tables and will not be included in the calculation of summary statistics or statistical analyses.

5.3.2. Handling of incomplete dates

5.3.2.1. Disease history

Incomplete dates for disease history (eg, initial diagnosis date, date of documented, locally advanced, inoperable or metastatic disease diagnosis, date of response or progression in prior treatment) will be imputed as follows:

- If the day is missing, it will be imputed to the 15th day of the month.
- If both day and month are missing and the year is prior to the year of the first study treatment, the month and day will be imputed as July 1st.
- If both day and month are missing and the year is same as the year of the first study treatment, the month and day will be imputed as January 1st.
- If the date is completely missing, no imputation will be performed.

